4.2.5 Analysis of Safety Variables

All safety analyses will be conducted on the safety population (i.e., all participants in the AUS ITT Population except those who return all pills delivered).

Duration of Treatment

Summary statistics for duration of treatment by days for the investigational product will be presented by overall and categorized by days of treatment 0-<30d, 30 - <60d, 60 - <90d, 90 - <120d, 120 - <150d, 150 - <180d, and those equal to or greater than 180 days.

Adverse Events

All AEs will be documented and recorded during the treatment period of the study, and during the follow-up period of the study. These two distinct time periods will be annotated in their respective tables.

Treatment Period:

Adverse events will be considered Treatment Period related if they fulfil one of the following criteria:

- Adverse events with an onset date on or after drug delivery date through Visit 2 or, if Visit 2 is not available, date of last contact
- Worsening of pre-existing events on or after drug delivery date
- Adverse events starting during treatment period and extending into 30-day follow-up period

Follow-Up Period:

Adverse events will be considered Follow-Up Period related if they occur after Visit 2.

For each time period, a summary table will be constructed to display the number of participants with at least one AE, the number of AEs by severity, the number of AEs possibly related to study drug, the number of serious AEs possibly related to study drug, the number of participants experiencing at least one serious AE, the number of participants with an AE leading to withdrawal from study, the number of participants with an AE leading to discontinuation of IP, and the number of AEs with outcome of death, and AEs by common terminology criteria for adverse events (CTCAE), along with key subject information.

The number and percentage of participants with at least one AE will be summarized by system organ class (SOC) and by preferred term (PT) within SOC.

The number and percentage of participants with at least one AE will be summarized by decreasing frequency on PT.

In addition, tables will be constructed to summarize AEs by severity.

Additionally, the number and percentage of participants with most common AEs, defined as those PTs with frequency $\geq 5\%$, will be summarized by SOC and by PT within SOC during the treatment period. This analysis will be repeated for the follow-up period.

All AEs will be listed.

4.2.6 Other Relevant Data Analysis/Summaries

4.2.6.1 Subject and Participant Disposition

A subject and participant disposition table will be constructed to show the various populations that will be evaluated in this study. The pre-screen failure population will be assessed based on the various categories of pre-screen failures possible. The subject disposition in the Pre-screen failure population will be presented based on the category of pre-screen failure. The reasons for pre-screen failures will be presented for those categories where data is available (i.e., inclusion/exclusion failures, qualified but refused to participate and subjects who failed TASS assessments).

The number of AUS screen failures, withdrawals, and discontinuations from study treatment in the SS population will be presented along with the associated reasons. Additionally, the number of participants who are lost to follow-up will be provided.

4.2.6.2 Concomitant Medication

All concomitant medications will be coded with the WHO Drug Dictionary. Tables will be constructed with counts and percentages of participants by anatomical therapeutic chemical ATC level 4 and preferred term at baseline (overall and by subgroups), in the treatment period and follow-up period.

4.2.6.3 Protocol Deviation

Protocol deviations will be summarized using all participants in the study database. The following criteria will be reported by count and percentages: participants with at least one important protocol deviation; related to the inclusion or exclusion criteria; discontinuation criteria and deviations related to study procedure.

5 INTERIM ANALYSES

Not applicable.

6 EXPLORATORY ANALYSES

6.1 Analysis of Risk Enhancing Factors

REFs will be evaluated based on the ASCVD and presence of these factors. These analyses will be a part of the Supplemental Statistical Analysis Plan.

7 CHANGES OF ANALYSIS FROM PROTOCOL

Not applicable.

¹³ Pellowe E, Salako K, Snelling S, Urdaibay C, Weston C. Daily variability in waist measurement. *Heart.* 2010;96(7):550. doi: 10.1136/hrt.2009.179242.

9 APPENDIX A - TABLE OF SCENARIOS FOR INADEQUATE LDL-C TASS ENTRIES ENTERED BY PARTICIPANT THAT COULD IMPACT CMOG TASS ENTRIES

For participants who 1) come to Visit 2 with an “OK to Use” outcome or an “Ask a Doctor” outcome and indicate the physician gave them permission to use the drug, 2) entered an initial retest that resulted in an Inadequate Response LDL-C and 3) made a purchase at the time they entered their initial Inadequate Response LDL-C retest, a second verified LDL-C retest will be required. If the participant does not obtain a second verified LDL-C retest or does not obtain a repeat LDL-C retest through SMT, their final use outcome will be “Missing” in situations where the CMOG receives a DNU outcome due to an “Inadequate Decrease on Follow-Up LDL-C Retest.”

For participants who come to Visit 2 with a “Do Not Use” outcome or an “Ask a Doctor” outcome and does not indicate their clinician gave them permission to use the drug, a second verified LDL-C retest will not be required following an Inadequate Response retest. In these instances, the CMOG will also be unable to determine an “OK to Use” outcome due to the lack of a verified LDL-C retest with an adequate response.

The following Table illustrates the potential scenarios where the participant enters an initial Inadequate Response LDL-C Retest into the Web App and purchases an additional supply of medication during their reorder assessment.

TABLE A1

Scenario	Participant LDL-C		Participant Final TASS Outcome	SMT Required (Y/N)	SMT Obtained (Y/N)	LDL-C (v)* input by CMOG	CMOG TASS Outcome	Coded Outcome	Is there a potential for a priori mitigation “Missing LDL- C Retest”?
	Value 1 (1 st retest)	Value 2 (2 nd retest)							
1a	IR (v)	-	OK to Use	Y	Y	SMT	If SMT is IR: DNU Kickout Reason: Inadequate Decrease on Follow Up LDL Cholesterol Retest If SMT is NR: DNU Kickout Reason: Increase or No Decrease in LDL Cholesterol	Same as CMOG TASS Outcome	No

Scenario	Participant LDL-C		Participant Final TASS Outcome	SMT Required (Y/N)	SMT Obtained (Y/N)	LDL-C (v)* input by CMOG	CMOG TASS Outcome	Coded Outcome	Is there a potential for a priori mitigation “Missing LDL-C Retest”?
	Value 1 (1 st retest)	Value 2 (2 nd retest)							
							If SMT is AR: OK to Use or Ask a Doctor		
1b	IR (v)	-	OK to Use	Y	N	IR (v) - Value 1	DNU Kickout Reason: Inadequate Decrease on Follow Up LDL Cholesterol Retest	DNU outcome coded to Missing due to lack of two verified IR LDL-C values to determine final outcome	Yes
2a	IR (v)	-	Ask a Doctor and Doctor Confirmed it is OK to Continue	Y	Y	SMT	If SMT is IR: DNU Kickout Reason: Inadequate Decrease on Follow Up LDL Cholesterol Retest If SMT is NR: DNU	Same as CMOG TASS Outcome	No

Scenario	Participant LDL-C		Participant Final TASS Outcome	SMT Required (Y/N)	SMT Obtained (Y/N)	LDL-C (v)* input by CMOG	CMOG TASS Outcome	Coded Outcome	Is there a potential for a priori mitigation “Missing LDL-C Retest”?
	Value 1 (1 st retest)	Value 2 (2 nd retest)							
							Kickout Reason: Increase or No Decrease in LDL Cholesterol If SMT is AR: OK to Use OR Ask a Doctor		
2b	IR (v)	-	Ask a Doctor and Doctor Confirmed it is OK to Continue	Y	N	IR (v) - Value 1	DNU Kickout Reason: Inadequate Decrease on Follow Up LDL Cholesterol Retest	DNU outcome coded to Missing due to lack of two verified IR LDL-C values to determine final outcome	Yes
3a	IR	-	OK to Use	Y	Y	SMT	If SMT is IR: DNU Kickout Reason: Inadequate	DNU outcome for IR result coded to Missing due to lack of two verified IR LDL-	Yes

Scenario	Participant LDL-C		Participant Final TASS Outcome	SMT Required (Y/N)	SMT Obtained (Y/N)	LDL-C (v)* input by CMOG	CMOG TASS Outcome	Coded Outcome	Is there a potential for a priori mitigation “Missing LDL-C Retest”?
	Value 1 (1 st retest)	Value 2 (2 nd retest)							
							Decrease on Follow Up LDL Cholesterol Retest If SMT is NR: DNU Kickout Reason: Increase or No Decrease in LDL Cholesterol If SMT is AR: OK to Use or Ask a Doctor	C values to determine final outcome Otherwise, same as CMOG TASS Outcome	
3b	IR	-	OK to Use	Y	N	No verified retest can be entered	OK to Use	“OK to Use” outcome coded to Missing due to a missing verified LDL-C retest value	Yes
4a	IR	-	Ask a Doctor and	Y	Y	SMT	If SMT is IR: DNU	DNu outcome for IR result coded to Missing due to lack of two verified IR LDL-	Yes

Scenario	Participant LDL-C		Participant Final TASS Outcome	SMT Required (Y/N)	SMT Obtained (Y/N)	LDL-C (v)* input by CMOG	CMOG TASS Outcome	Coded Outcome	Is there a potential for a priori mitigation “Missing LDL- C Retest”?
	Value 1 (1 st retest)	Value 2 (2 nd retest)							
			Doctor Confirmed it is OK to Continue				
Kickout Reason: Inadequate Decrease on Follow Up LDL Cholesterol Retest
 
If SMT is NR: DNU
 
Kickout Reason: Increase or No Decrease in LDL Cholesterol
 
If SMT is AR: OK to Use or Ask a Doctor
	C values to determine final outcome Otherwise, same as CMOG TASS Outcome	
4b	IR	-	Ask a Doctor and Doctor Confirmed it is OK to Continue	Y	N	No verified retest can be entered	Ask a Doctor and Doctor Confirmed it is OK to Continue	“ Ask a Doctor and Doctor Confirmed it is OK to Continue ” outcome coded to Missing due to a	Yes

Scenario	Participant LDL-C		Participant Final TASS Outcome	SMT Required (Y/N)	SMT Obtained (Y/N)	LDL-C (v)* input by CMOG	CMOG TASS Outcome	Coded Outcome	Is there a potential for a priori mitigation “Missing LDL-C Retest”?
	Value 1 (1 st retest)	Value 2 (2 nd retest)							
								missing verified LDL-C retest value	
5	IR (v)	IR	DNU Kickout Reason: Inadequate Decrease on Follow Up LDL Cholesterol Retest	N	-	IR (v) - Value 1	DN Kickout Reason: Inadequate Decrease on Follow Up LDL Cholesterol Retest	DN outcome coded to Missing due to lack of two verified IR LDL-C values to determine final outcome	No
6	IR	IR (v)	DNU Kickout Reason: Inadequate Decrease on Follow Up LDL Cholesterol Retest	N	-	IR (v) - Value 2	DN Kickout Reason: Inadequate Decrease on Follow Up LDL Cholesterol Retest	DN outcome coded to Missing due to lack of two verified IR LDL-C values to determine final outcome	No
7a	IR (v)	AR	OK to Use	Y	Y	SMT	If SMT is IR: DN Kickout Reason: Inadequate Decrease on	Same as CMOG TASS Outcome	No

Scenario	Participant LDL-C		Participant Final TASS Outcome	SMT Required (Y/N)	SMT Obtained (Y/N)	LDL-C (v)* input by CMOG	CMOG TASS Outcome	Coded Outcome	Is there a potential for a priori mitigation “Missing LDL- C Retest”?
	Value 1 (1 st retest)	Value 2 (2 nd retest)							
							Follow Up LDL Cholesterol Retest If SMT is NR: DNU Kickout Reason: Increase or No Decrease in LDL Cholesterol If SMT is AR: OK to Use or Ask a Doctor		
7b	IR (v)	AR	OK to Use	Y	N	IR (v) - Value 1	DNU Kickout Reason: Inadequate Decrease on Follow Up LDL Cholesterol Retest	DNU outcome coded to Missing due to lack of two verified IR LDL-C values to determine final outcome	Yes

Scenario	Participant LDL-C		Participant Final TASS Outcome	SMT Required (Y/N)	SMT Obtained (Y/N)	LDL-C (v)* input by CMOG	CMOG TASS Outcome	Coded Outcome	Is there a potential for a priori mitigation “Missing LDL-C Retest”?
	Value 1 (1 st retest)	Value 2 (2 nd retest)							
8	IR (v)	NR	DNU Kickout Reason: Increase or No Decrease in LDL Cholesterol	N	-	IR (v) - Value 1	DNU Kickout Reason: Inadequate Decrease on Follow Up LDL Cholesterol Retest	DNU outcome coded to Missing due to lack of two verified IR LDL-C values to determine final outcome	No
9a	IR	AR	OK to Use	Y	Y	SMT	If SMT is IR: DNU Kickout Reason: Inadequate Decrease on Follow Up LDL Cholesterol Retest If SMT is NR: DNU Kickout Reason: Increase or No Decrease in LDL Cholesterol	DNU outcome for IR result coded to Missing due to lack of two verified IR LDL-C values to determine final outcome Otherwise, same as CMOG TASS Outcome	Yes

Scenario	Participant LDL-C		Participant Final TASS Outcome	SMT Required (Y/N)	SMT Obtained (Y/N)	LDL-C (v)* input by CMOG	CMOG TASS Outcome	Coded Outcome	Is there a potential for a priori mitigation “Missing LDL- C Retest”?
	Value 1 (1 st retest)	Value 2 (2 nd retest)							
							If SMT is AR: OK to Use or Ask a Doctor		
9b	IR	AR	OK to Use	Y	N	No verified retest can be entered	OK to Use	“OK to Use” outcome coded to Missing due to a missing verified LDL-C retest value	Yes
10	IR (v)	IR (v)	DN Kickout Reason: Inadequate Decrease on Follow Up LDL Cholesterol Retest	N	-	IR (v) - Value 2	DN Kickout Reason: Inadequate Decrease on Follow Up LDL Cholesterol Retest	Same as CMOG TASS Outcome	No
11	IR	IR	DN Kickout Reason: Inadequate Decrease on Follow Up LDL Cholesterol Retest	N	-	No verified retest can be entered	OK to Use	“OK to Use” outcome coded to Missing due to a missing verified LDL-C retest value	No

Scenario	Participant LDL-C		Participant Final TASS Outcome	SMT Required (Y/N)	SMT Obtained (Y/N)	LDL-C (v)* input by CMOG	CMOG TASS Outcome	Coded Outcome	Is there a potential for a priori mitigation “Missing LDL- C Retest”?
	Value 1 (1 st retest)	Value 2 (2 nd retest)							
12	IR	AR (v)	OK to Use	N	-	AR (v) - Value 2	OK to Use	Same as CMOG TASS Outcome	No
13	IR (v)	AR (v)	OK to Use	N	-	AR (v) - Value 2	OK to Use	Same as CMOG TASS Outcome	No
14	IR (v)	NR (v)	DNU Kickout Reason: Increase or No Decrease in LDL Cholesterol	N	-	N (v) - Value 2	DNU Kickout Reason: Increase or No Decrease in LDL Cholesterol	Same as CMOG TASS Outcome	No
15	IR	NR (v)	DNU Kickout Reason: Increase or No Decrease in LDL Cholesterol	N	-	N (v) - Value 2	DNU Kickout Reason: Increase or No Decrease in LDL Cholesterol	Same as CMOG TASS Outcome	No
16	IR	NR	DNU Kickout Reason: Increase or No	N	-	No verified retest can be entered	OK to Use	“OK to Use” outcome coded to Missing due to a missing verified LDL-C retest value	

Scenario	Participant LDL-C		Participant Final TASS Outcome	SMT Required (Y/N)	SMT Obtained (Y/N)	LDL-C (v)* input by CMOG	CMOG TASS Outcome	Coded Outcome	Is there a potential for a priori mitigation “Missing LDL- C Retest”?
	Value 1 (1 st retest)	Value 2 (2 nd retest)							
			Decrease in LDL Cholesterol						No

IR – Inadequate LDL-C Response; AR – Adequate LDL-C Response; NR – No Response (i.e., Zero Percent lowering or increase in LDL-C); v – verified source; DNU – Do Not Use; SMT – Study Mandated Test; UTD – Unable to Determine

*The CMOG will always enter the most recent verified LDL-C retest from the Diagnostic Form for their TASS assessment.

The following Table illustrates the potential scenarios where the participant enters an initial Inadequate Response LDL-C Retest into the Web App and **does not** purchase an additional supply of medication during their reorder assessment. In these situations, the clinician Web App experience will be the same as the participant experience at the time they entered the inadequate LDL-C response value into the Web App.

TABLE A2

Scenario	Participant LDL-C		Participant Final TASS Outcome	SMT Required (Y/N)	SMT Obtained (Y/N)	LDL-C (v)* input by CMOG	CMOG TASS Outcome	Coded Outcome	Is there a potential for a priori mitigation “Missing LDL-C Retest – Rationale #3”?
	Value 1	Value 2							
1**	IR (v)		OK to Use	N	-	IR (v)	OK to Use	Same as CMOG TASS Outcome	No
2**	IR		OK to Use	N	-	No verified retest can be entered	Ok to Use	Same as CMOG TASS outcome	No
3	IR (v)	-	Ask a Doctor and Doctor DOES NOT Confirm it is OK to Continue	N	-	IR (v) - Value 1	Ask a Doctor and Doctor DOES NOT Confirm it is OK to Continue	Same as CMOG TASS Outcome	No

Scenario	Participant		Participant Final TASS Outcome	SMT Required (Y/N)	SMT Obtained (Y/N)	LDL-C (v)* input by CMOG	CMOG TASS Outcome	Coded Outcome	Is there a potential for a priori mitigation “Missing LDL-C Retest – Rationale #3”?
	Value 1	Value 2							
4	IR	-	Ask a Doctor and Doctor DOES NOT Confirm it is OK to Continue	N	N	No verified retest can be entered	Ask a Doctor and Doctor DOES NOT Confirm it is OK to Continue	“Same as CMOG TASS Outcome	No

IR – Inadequate LDL-C Response; AR – Adequate LDL-C Response; NR – No Response (i.e., Zero Percent lowering or increase in LDL-C); v – verified source; DNU – Do Not Use; SMT – Study Mandated Test; UTD – Unable to Determine

*The CMOG will always enter the most recent verified LDL-C retest from the Diagnostic Form for their TASS assessment.

**Scenarios 1 and 2 are discontinuation scenarios.

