As mentioned in [Section 3.2.1](#), during the use phase of the study participants will be asked about their repeat LDL-C test to ensure they are getting an adequate therapeutic response. The participant's behavior with regard to retesting as well as the LDL-C value entered into the Web App contribute to their final use assessment. Participants are permitted to enter any LDL-C value into the Web App and are not told that the values will be source verified until Virtual Visit 2. If they are unable to provide a source document for a value, they will have a SMT. In contrast, the CMOG clinician will only be permitted to enter source verified LDL-C data into the Web App for their assessments. This is done to prevent a CMOG final use assessment based on an inaccurate LDL-C. Following feedback from FDA, the Web App was programmed to take specific actions based on whether a participant retested and based on the result of a retest. The actions are as follows:

- If the participant fails to enter a retest, they can continue to reorder provided they do not indicate within the Web App that they experienced another condition that would prevent them from reordering. Participants who continue to receive an “OK to Use” outcome or an “Ask a Doctor” outcome and indicate that the doctor gave them permission to use the drug, and do not voluntarily retest, will have a study mandated LDL-C test performed prior to Virtual Visit 2. This SMT will be used by the clinician for their assessment but will not be used by the participant since they did not voluntarily get tested.
- If the participant enters an LDL-C value into the Web App, the following can occur:
 - If the value demonstrates an adequate LDL-C response (i.e., $\geq 15\%$ reduction), the participant will proceed in the study and will no longer be prompted to enter an LDL-C into the Web App.
 - If the value demonstrates no change or an increase in LDL-C, the participant will get a “Do Not Use” outcome and will be scheduled for Virtual Visit 2 where all procedures except a SMT will be performed. If the participant fails to bring verification of the LDL-C test that resulted in stopping drug, the CMOG clinician will leave the LDL-C field in the Web App blank. The CMOG use assessment would result in an “OK to Use” outcome. However, when a subject who has continued in the study for 3 or more months fails to obtain a verified LDL-C

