retest for use by the CMOG at Visit 2, an “OK to Use” outcome by the CMOG will be coded as missing since the lack of an LDL-C value means the CMOG can never know for certain that the subject was truly “OK to Use”. The need to recode the CMOG outcome in this instance is a function of the Web App being programmed to allow all subjects to complete the 6 months study regardless of whether they obtained an LDL-C retest. In those situations where the participant has been in the study less than 3 months, a verified LDL-C will not be required for the CMOG to determine an outcome since the DFL allows individuals up to 3 months to obtain an LDL-C retest.

- If the value demonstrates an inadequate LDL-C response (i.e., $\geq 0\%$ and $< 15\%$ reduction), the participant will get an “OK to Use” outcome and be able to order drug, but they will be asked to repeat the LDL-C test. Therefore, individuals with an inadequate response, who proceed to purchase more medication, may have more than one LDL-C value entered into the Web App during the course of the study and the second LDL-C value entered into the Web App could result in one of the following outcomes:
 - If the result is an inadequate response or an increase in LDL-C, the participant will get a “Do Not Use” outcome.
 - If the result is an adequate response, the participant will get an “OK to Use” outcome.
 - If no additional LDL-C value is entered into the Web App, the participant will continue to get an “OK to Use” outcome.

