- For a CMOG final use outcome to be determined as “Ok to Use”, all answers to the questions associated with Do Not Use and Ask a Doctor warnings must be answered as “No”. By default, an “Ok to Use” final use outcome can only be obtained when the CMOG clinician has answers to all the questions that are asked in the TASS tool. This includes having an LDL-C retest with an adequate response for participants who have continued in the study for 3 or more months. Thus, all “OK to Use” final use outcomes should be coming via a TASS assessment.

In those instances where a participant, CMOG or both TASS assessments are missing such that an Overall Final Use Outcome cannot be determined, the impact of the missing information will be assessed using the prespecified sensitivity analyses (see [Section 4.2.2](#)).

Missing CMOG initial TASS assessments should be rare or non-existent. In the event the CMOG is unable to perform a TASS assessment at Visit 1, the CMOG clinician will use the

DFL and follow an algorithm based on the question flow of the TASS tool to make a determination as described above. If the CMOG is unable to make a determination, the initial outcome will be missing.

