Participant has “Do Not Use” warning and withdraws from study	Participant identifies “Do Not Use” warning from DFL or through TASS but does not complete sufficient medical and medication history or all assessments associated with Virtual Visit 2 to obtain a final use outcome	AUS ITT	Withdrawal	Insufficient data to assess Clinician final use outcome is “Missing”
Participant has “Do Not Use” warning and does not stop use	Participant does not identify “Do Not Use” warning and completes sufficient medical and medication history or all assessments associated with Virtual Visit 2 to obtain a final use outcome	PP	Completed	Incorrect

Scenario	Action	Analysis Population	Study Disposition	Assessment for Overall Correct Final Use Outcome*
Participant has an “OK to Use” outcome which CMOG cannot confirm because of the lack of a verified LDL-C retest and participant has been in study <3 months	Because participant has up to 3 months to obtain an LDL-C retest, the CMOG can obtain an “OK to Use” outcome without the need for a verified LDL-C retest value	PP	Completed	Correct, Incorrect or Mitigated
Participant has an “OK to Use” outcome which CMOG cannot confirm because of the lack of a verified LDL-C retest and participant has been in study >3 months	A CMOG final use outcome cannot be obtained due to the lack of a verifiable LDL-C value	AUS ITT	Withdrawal	Insufficient data to assess If CMOG obtains “OK to Use” outcome, the CMOG outcome will be changed to “Missing”. An a priori mitigation for missing LDL-C is possible in this situation
Participant decides to withdraw from study	Participant does not complete sufficient medical and medication history or all assessments associated with Virtual Visit 2 to obtain a final use outcome	AUS ITT	Withdrawal	Insufficient data to assess Participant and Clinician final use outcomes are “Missing.”
Participant is Lost to Follow-Up (LTf)	Participant does not complete sufficient medical and medication history or all assessments associated with Virtual Visit 2 to obtain a final use outcome	AUS ITT	Lost to Follow-Up	Insufficient data to assess Participant and Clinician final use outcomes are “Missing.”

*The mitigation process is the same as the overall mitigation process for the study.

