
Missing LDL-C Retests
 
 - Given consumers can only purchase non-prescription rosuvastatin through the Web App, we can stop shipping medication to individuals who fail to retest after a period of time agreed with FDA. Thus, for participants who qualify for treatment (i.e., have an “OK to Use” outcome or an “Ask a Doctor” outcome and indicates the doctor gave them permission to use the drug) but fail to obtain the necessary verified retest(s) (whether it is an initial retest or a second retest in those with an inadequate response), an a priori mitigation allowing these individuals to be mitigated to a “correct” response is appropriate. This mitigation can only be applied in situations where the CMOG’s outcome was “coded” as “missing” because of a missing LDL-C value, and the CMOG’s TASS outcome would have matched the Participant Outcome if not for the missing LDL-C retest. 	
 1. CMOG final TASS assessment is “OK to Use” or “Ask a Doctor”, but is coded as “Missing” because the participant failed to obtain a verified LDL-C retest or an SMT. 2. CMOG final TASS assessment is “OK to Use” but coded as “Missing” because the participant failed to retest and the SMT was an Inadequate Response, or the participant self-tested with a verified inadequate response result that was used for their Visit 2 reassessment. 3. Participant enters an initial Inadequate Response LDL-C retest into the Web App (verified or unverified), has an “OK to Use” outcome or “Ask a Doctor” outcome, indicates the doctor gave them permission to use the drug and makes a purchase. CMOG final TASS assessment is coded as “Missing” because only one or no verified LDL-C retest value was available for use, but otherwise would have matched the participant outcome. (Table XX, scenarios 1b, 2b, 3a, 3b, 4a, 4b, 7b, 9a, 9b)

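### SAP Table A2 scenario 2 keeps a clinician OK to Use outcome with no verified LDL-C retest and no time limit, while other SAP rules code it Missing from 3 months

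*SAP*

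**What the plan says.** Table A2 in SAP Appendix A deals with participants who enter an inadequate LDL-C retest and do not buy more drug at that reorder assessment. In scenario 2 the participant's final outcome is OK to Use, no study mandated test is required, and for the clinician's LDL-C input the table states "No verified retest can be entered". The clinician's outcome is OK to Use, and the coded-outcome column leaves it as it is: "Same as CMOG TASS Outcome" (scenario 2 differs only in a lower-case last word). The mitigation column, which refers only to Rationale #3, says No. A footnote adds: "Scenarios 1 and 2 are discontinuation scenarios". No row carries a time-in-study condition.

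Other parts of the SAP treat the same state differently:

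- **Section 3.2.3** applies "when a subject who has continued in the study for 3 or more months fails to obtain a verified LDL-C" retest for the clinician's use at Visit 2. In that case "an “OK to Use” outcome by the CMOG will be coded as missing since the lack of an LDL-C value" leaves the clinician unable to confirm it. The one exemption stated is for participants in the study less than 3 months.
- **Section 3.2.3.3**, on what a clinician OK to Use outcome requires: "This includes having an LDL-C retest with an adequate response for participants who have continued in the study for 3 or more months".
- **Appendix B**, for an OK to Use outcome that the clinician cannot confirm for lack of a verified retest after more than 3 months: "If CMOG obtains “OK to Use” outcome, the CMOG outcome will be changed to “Missing".
- **Table A1, scenario 3b**: the same unverified inadequate entry, no study mandated test obtained and the same clinician outcome, but after a purchase. It is coded Missing.

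**The concern.** For a participant at 3 months or more, a programmer working from Table A2 keeps OK to Use, and one working from Section 3.2.3 or Appendix B sets Missing. Both are following the SAP, and the variable feeds a co-primary endpoint.

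The two codes lead to different places. If OK to Use stands, participant and clinician agree, and Figure 2 of the SAP makes the case a Correct Selection with no mitigation involved. It then stays Correct in the Per Protocol evaluation without mitigations and does not appear in the tables counting mitigated participants. If it is coded Missing, Section 4.2.2 drops it from numerator and denominator, and any later credit has to come through Appendix D, where it is counted. SAP 3.2.3.1 says the runs with and without mitigations are there to show the impact of mitigation. Under Table A2, some credit given without a verified LDL-C does not show up in that comparison.

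**Working it through.** **1. The plan's own figure.** SAP 1.3 gives n = 500, a true rate of 90% and a two-sided 95% Clopper-Pearson lower bound (LB) that must exceed 85%, with at least 90% power. The smallest passing count is 441/500 = 88.2% (LB 85.04%); 440/500 gives LB 84.82%. Power = P(X ≥ 441 | n = 500, p = 0.90) = 91.9%, so the stated figure reproduces.

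**2. Same LDL-C data, different code.**

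| Place in SAP | Verified retest | Clinician outcome | Time condition | Coded |
|---|---|---|---|---|
| Table A2, scenario 2 | none | OK to Use | none | OK to Use |
| Table A1, scenario 3b | none | OK to Use | none | Missing |
| Section 3.2.3 | none | OK to Use | 3 months or more | Missing |
| Appendix B | none | OK to Use | over 3 months | Missing |
| Appendix D, rationale 1 | none | OK to Use | none | Missing, may be mitigated |

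Scenarios 3b and 2 differ in whether a purchase followed the entry. A purchase does not change what the clinician knows about the LDL-C.

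**3. Effect on the run without mitigations.** Let k be the number of scenario 2 cases at 3 months or more. The documents do not give it, so k = 5 to 25 of 500 is an assumption. With x counted Correct under Table A2:

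- Table A2 coding: rate = x/500
- Missing coding: rate = (x − k)/(500 − k)

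With about 86% correct among the other participants (assumed):

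| k | Missing coding | Table A2 coding | Difference |
|---|---|---|---|
| 5 | 426/495 = 86.06% | 431/500 = 86.20% | 0.14 points |
| 15 | 417/485 = 85.98% | 432/500 = 86.40% | 0.42 points |
| 25 | 408/475 = 85.89% (LB 82.4%) | 433/500 = 86.60% (LB 83.3%) | 0.71 points |

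Starting from the planned 90%, 450/500 (LB 87.03%):

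| k | Missing coding | LB |
|---|---|---|
| 10 | 440/490 = 89.8% | 86.77% |
| 25 | 425/475 = 89.5% | 86.36% |
| 50 | 400/450 = 88.9% | 85.61% |
| 75 | 375/425 = 88.2% | 84.79% |

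**4. When the lower bound crosses 85%.** The smallest k that takes it from above 85% to below:

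| Correct under Table A2 | Smallest k |
|---|---|
| 441/500 | 2 (439/498, LB 84.98%) |
| 445/500 | 32 |
| 450/500 | 69 |
| 455/500 | 107 |

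**5. Effect on the mitigated primary analysis.** Rationale 1 in Appendix D lets a clinician OK to Use that was coded Missing for want of a verified retest be mitigated to correct, provided the outcomes would otherwise have matched. In scenario 2 they do match. Recoding to Missing followed by mitigation therefore returns the case to Correct.

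**The case against.** The strongest defence is that Table A2 is the specific rule. SAP 3.2.3 sends the reader to Appendix A for how inadequate-response scenarios are managed, and the footnote limits scenarios 1 and 2 to discontinuers. Section 3.2.3 justifies the recode by the Web App letting everyone finish 6 months, which is a reason about completers. The Appendix B row carries the disposition Withdrawal, which the documents distinguish from discontinuation. This reading is available, but the SAP does not state it. The footnote gives no coding exception, and the only exemption in Section 3.2.3 is for time in study. Nor can the absence of a study mandated test be the reason: Table A1 scenarios 11 and 16 require no such test and are still coded Missing.

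The group is also narrow. A case needs an inadequate entry, no purchase, discontinuation, 3 months in study and a participant outcome of OK to Use. Discontinuers who decline a final assessment can be coded only Do Not Use or Ask a Doctor under SAP 3.2.3.3, so they never reach this row. That stands and keeps the effect small.

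A reader might infer that scenario 1 is the same error. It is not clearly so, because there the inadequate value is verified, and neither Section 3.2.3 on a lacking value nor the Appendix B row applies. Two places point to Missing. One is the adequate-response condition in 3.2.3.3, which sits in the fallback procedure for missing clinician assessments. The other is Appendix D rationale 2, which lists among outcomes coded Missing "or the participant self-tested with a verified inadequate response result that was used for their Visit 2 reassessment". Against them, SAP 3.2.3 gives OK to Use after a first inadequate value and says the clinician's experience mirrors that first entry when nothing was bought. The introduction to Appendix A asks for a second verified retest only after a purchase. The SAP's own passages conflict here, and the text does not settle which should prevail.

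**Conclusion.** The contradiction is real for scenario 2 at 3 months or more and should be resolved before the database is locked. Under 3 months there is no conflict. Appendix B speaks of over 3 months and Section 3.2.3 of 3 or more, so the boundary should be stated once.

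Its size is modest: about 0.1 to 0.7 points in the Per Protocol run without mitigations. That range rests on an assumed 5 to 25 cases among 500 and about 86% correct among the rest. The documents set no separate success criterion for that run, so the crossing of 85% near 441/500 affects how it reads, not trial success.

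Two stronger conclusions are tempting and unsupported. The first is that the primary result is inflated: Appendix D rationale 1 can restore Correct, so the fully mitigated result is largely unchanged and moves only where that rationale is not applied. The second is that each case shifts a worst-case AUS ITT analysis from Correct to Incorrect. That would need an unmitigated worst-case run. The SAP places the no-mitigation evaluation on the Per Protocol population and specifies no unmitigated version of the AUS ITT imputations. With mitigation applied, the planned worst-case run would barely move.

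**What to change.** In Table A2, limit the unchanged coded outcome in scenario 2 to participants under 3 months in study, and code it Missing at 3 months or more, as in Table A1 scenario 3b. Widen the table's mitigation column beyond Rationale #3 so that credit for these cases is recorded under Appendix D rationale 1, appears in the mitigation counts and drops out of the run without mitigations.

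For scenario 1, have the sponsor state which passages govern (3.2.3.3 and Appendix D rationale 2, or 3.2.3 and the introduction to Appendix A) and align the others. If it is to be coded Missing, say whether the 3-month condition applies, since rationale 2 has none.

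The cost is an edit to two table rows and the mitigation column, plus one coding condition, with no new data. The no-mitigation figure may become slightly less favourable.
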